5.8 Storage and Accountability

CAP-1002 (or placebo) will be shipped to sites as needed on an individual subject basis and only after a subject has (1) provided written informed consent, (2) met all eligibility criteria for entry into the study, (3) successfully completed all screening evaluations and 4) been randomized to receive either CAP-1002 or placebo treatment. The investigational products will not be stored at individual sites other than in the shipping materials provided by the Sponsor.

Detailed instructions for storage and handling are provided in the Instructions for Use that are included with each individual treatment shipment. Sites are instructed to hold the IP in its shipping container until it is dispensed just prior to infusion. The Sponsor will time delivery of the IP to the clinical sites such that the time in the shipping container is less than the known expiration time. **Once removed from the shipping container, the IP expires at 90 minutes post-removal.** An expiration time will be noted on the product at the time of removal and preparation. Investigators are instructed to store the IP at room temperature (approximately 25°C) and to administer the IP prior to the noted expiration time.

5.9 Investigational Product Retention at Study Site

Since IP will be delivered as needed on a per subject basis, there will be no IP to retain at the site. Site will be instructed to retain labels and packaging materials as part of the subject records. Should a subject be found unsuitable for infusion after IP has been shipped, the site is instructed to return the IP to the Sponsor's Manufacturing Facility per the Sponsor's instructions.

5.10 Investigational Product Accountability and Reconciliation

The Sponsor is responsible for IP accountability, reconciliation, and record maintenance. Training will be provided regarding IP accountability. In accordance with all applicable regulatory requirements, the designated study center personnel must maintain accountability records throughout the study, and the Sponsor (or, designee) will review IP accountability and reconciliation.

6 STUDY PROCEDURES

6.1 Informed Consent

Before being admitted to the clinical study, all subjects must consent in writing to participate. An Informed Consent Form (ICF) will be given to each subject, which will contain all United States federally required elements, all ICH-required elements, and Health Insurance Portability and Accountability Act (HIPAA) authorization information in language that is understandable to the subject. The process of obtaining the informed consent will be in compliance with all federal regulations, International Conference on Harmonisation (ICH) requirements, and local laws. Per this protocol, the subject may sign the ICF immediately post-MI (e.g., acute admission at hospital). The following assessments will be permitted within 28 days immediately following the subject's MI: signing ICF, review of medical history, review of concomitant medications, and collection of laboratory samples required for assessment of study eligibility criteria (e.g., eGFR, HbA1c, hepatitis serology, HIV serology, LFTs, hematocrit, WBC, and platelet count). All other screening tests, including the subject's cardiac MRI and CT (chest, abdomen, pelvis), must be conducted greater than 28 days post-MI. Infusion must occur within 28 days of the first screening procedure that is performed greater than 28 days post-MI. Relevant safety laboratory sample collections (e.g., chemistry, hematology, urinalysis) may need to be repeated as they must be obtained within 28 days of the subject's infusion. Additional instructions are included in protocol Section 7 and Appendix I (Schedule of Events).

The Investigator and/or designee must discuss the study with each subject. The discussion will include the nature, scope, procedures, and possible consequences of the subject's participation in the study. The ICF and review will be in a form understandable to the subject. The subject must be given adequate time to review the ICF and ask questions regarding the IP, procedures, risks and other treatment. The Investigator or designee and the subject must both sign and date the ICF after review and before the subject can participate in the study. The subject will receive a copy of the signed and dated form, and the original will be retained in the site study files. The Investigator or his/her designee will emphasize to the subject that study participation is entirely

voluntary and that consent regarding study participation may be withdrawn at any time without penalty or loss of benefits to which the subject is otherwise entitled.

If the ICF is amended during the study, the Investigator must follow all applicable regulatory requirements pertaining to approval of the amended ICF by the IRB/IEC. The site must use the amended consent form for all new subjects and repeat the consent process with the amended ICF for any ongoing subjects.

6.2 Medical History

The general and cardiac-specific medical histories (e.g., significant procedures, medications, therapies, allergies) of subjects enrolled in the study will be documented as part of the screening visit and reviewed during subsequent visits (e.g., day of infusion, follow-up visits) for any modifications (i.e., assessment for potential adverse events). General and cardiac health, as well as concomitant medications, will be reviewed and assessed at each subject visit and new information will be updated in the subject's study documentation.

6.3 Physical Examinations

A qualified physician, either the Investigator or Sub-Investigator, will perform a limited cardiovascular physical examination at each study visit which will include angina and arrhythmia assessments.

A limited physical examination will be conducted at the screening visit and the 12 Month follow-up visit. Height and weight will also be collected and recorded at screening; weight will be collected at all subsequent visits.

6.4 Vital Signs

Temperature, heart rate, blood pressure and respiration rate will be recorded at each visit on the case report form.

6.5 Clinical Laboratory Tests

6.5.1 Laboratory Parameters

Section 7 and Appendix I (Schedule of Events) list applicable clinical laboratory tests to be collected at study visits. Subjects will be in a seated or supine position during blood collection. Clinical laboratory tests will include the following:

Table 1. List of Laboratory Tests

| | |
|--|--|
| Hematology: | Serum Chemistry: |
| Hematocrit (Hct) | Alanine aminotransferase (ALT; SGPT) |
| Hemoglobin (Hgb) | Aspartate aminotransferase (AST; SGOT) |
| Platelet count | Blood urea nitrogen (BUN) |
| White blood cell (WBC) count with differential | Creatinine |
| Urinalysis: | Estimated Glomerular filtration rate (eGFR) |
| Appearance | Glucose |
| Bilirubin | Lactate dehydrogenase (LDH) |
| Color Glucose Ketones | Potassium (K) |
| Microscopic examination of sediment | Sodium (Na) |
| Nitrite | Hemoglobin A1c (HbA1c) (screening) |
| Occult blood pH | Troponin I or Troponin T if Troponin I is not available. |
| Protein | N-terminal pro-hormone brain natriuretic peptide (NT-proBNP) |
| Specific gravity | |
| Urobilinogen | |
| Serum beta human chorionic gonadotropin (hCG) (only for females who are not diagnosed as postmenopausal) | Coagulation [Infusion Visit only - for subjects taking warfarin (Coumadin®)]: |
| Donor Specific Antibody (DSA) monitoring and HLA (Human Leukocyte Antigen) typing | Activated partial thromboplastin time(PTT) International Normalized Ratio (INR) |
| ELISpot assay | |
| Serum Biomarkers (if subject provided consent) | Hepatitis B surface Antigen (HBsAg) (screening) Hepatitis C Virus (HCV) (screening) Human Immunodeficiency Virus (HIV) (screening) |

6.5.2 Sample Collection, Storage, and Shipping

Laboratory studies will be performed and reported at each individual study site, with the exception of the following:

Serum for the donor specific antibody (DSA) monitoring, HLA typing and blood for the ELISpot assay will be collected and processed at each site and then shipped to a central core laboratory for analysis within 24 hours of obtaining the specimens (See Laboratory Manual for shipping instructions). Subjects will be monitored for the development of a cellular immune response using the ELISpot (enzyme-linked immunosorbent spot) assay. The ELISpot assay will be performed at screening and at the one month study visit in a total of 50 patients treated with CAP-1002 (and concurrently 18 placebo subjects: 14 open-label CDC subjects, 36 randomized CDC subjects, 18 randomized placebo subjects) and will be reviewed by the DSMB. If the DSMB determines that there is reason to believe additional value would be gained from a larger sample of subjects, ELISpot testing will be performed for additional subjects, followed by additional, subsequent DSMB review.

- Serum for research purposes (biomarkers) will be collected and processed at each site then shipped to a central core lab that will then ship to Capricor for final storage and analysis (if subject has provided consent).

Individual sites will be instructed regarding the processing and shipping procedures.

6.6 12-Lead ECG

Beginning at the screening visit, a 12-Lead ECG will be performed at every study visit to assess for rhythm disturbances and new myocardial ischemia or infarction. Subsequent ECGs will be compared with the screening ECG for any changes in rhythm and conduction. All changes and any associated clinical significance will be evaluated and documented on the case report forms.

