9.5 Primary Endpoint(s)

9.5.1 Primary Safety Endpoint(s)

Medical Dictionary for Regulatory Activities (MedDRA) will be used for this study to code adverse events.

The primary safety endpoint is the proportion of subjects experiencing any of the following adjudicated events within one month following intracoronary infusion:

1. Acute myocarditis possibly attributable to CAP-1002 or placebo, diagnosed with consideration of clinical context, with or without a clinically indicated endomyocardial biopsy. In order to be considered related to CAP-1002 or placebo, humoral or cellular immune reaction specific to CAP-1002 must also be documented for subjects treated with CAP-1002, or a temporal relationship with IP administration must exist for subjects administered placebo.
2. Death due to ventricular tachycardia or ventricular fibrillation defined as occurring with ECG documentation of these arrhythmias during ambulatory ECG monitoring in an outpatient setting, or during routine ECG monitoring while hospitalized.
3. Sudden unexpected death defined as occurring within one hour of symptom onset, or unwitnessed death in a person previously observed to be well within the preceding 24 hours without an identified cause.
4. Major adverse cardiac event (MACE), defined as the composite incidence of death, non-fatal recurrent MI, hospitalization for heart failure, emergency room treatment for heart failure (NT-proBNP >450 pg/mL or BNP >100 pg/ml, with treatment including intravenous diuretic administration), left ventricular assist device (LVAD) placement or heart transplant. Peri-infusion MI will be defined as presence of troponin or CK-MB levels > 5 times the upper reference limit during the 24 hours following infusion. These elevations must be

accompanied by symptoms of ischemia >20 minutes in duration and ECG changes indicative of new ischemia (new ST-T changes or new left bundle branch block), development of pathological Q waves on the ECG, imaging evidence of new loss of viable myocardium, or new regional wall motion abnormality.

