9.6 Secondary Endpoint(s)

9.6.1 Secondary Safety Endpoint(s)

The following adjudicated events will be evaluated as secondary safety endpoints during the twelve-month follow-up period:

1. Acute myocarditis possibly attributable to CAP-1002 or placebo, diagnosed with consideration of clinical context, with or without a clinically indicated endomyocardial biopsy. In order to be considered related to CAP-1002 or placebo, humoral or cellular immune reaction specific to CAP-1002 must also be documented for subjects treated with CAP-1002, or a temporal relationship with IP administration must exist for subjects administered placebo.
2. Death due to ventricular tachycardia or ventricular fibrillation defined as occurring with prior ECG documentation of these arrhythmias during ambulatory ECG monitoring in an outpatient setting or during routine ECG monitoring while hospitalized.
3. Sudden unexpected death defined as occurring within one hour of symptom onset, or unwitnessed death in a person previously observed to be well within the preceding 24 hours without an identified cause.
4. Major adverse cardiac event (MACE), defined as the composite incidence of death, non-fatal recurrent MI, hospitalization for heart failure, emergency room treatment for heart failure (NT-proBNP >450 pg/mL or BNP>100 pg/ml, with treatment including intravenous diuretic administration), left ventricular assist device (LVAD) placement or heart transplant. Peri-infusion MI will be defined as presence of troponin or CK-MB levels > 5 times the upper reference limit during the 24 hours following infusion. These elevations must be accompanied by symptoms of ischemia > 20 minutes in duration and ECG changes indicative of new ischemia (new ST-T changes or new left bundle branch block), development of pathological Q waves on the ECG, imaging evidence of new loss of viable myocardium, or

new regional wall motion abnormality.

5. New cardiac tumor formation on MRI imaging.
6. Any hospitalization due to a cardiovascular cause or related to CAP-1002 or placebo infusion.
7. Any inter-current cardiovascular illness or one related to CAP-1002 or placebo infusion, which prolongs hospitalization. Evidence of myocardial injury will be assessed by a rule out MI cardiac enzyme protocol performed following administration of CAP-1002 or placebo. Troponin and CK-MB will be obtained approximately every 8 hours for the first 24 hours after infusion.

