### 2.3 Study Endpoints and Hypotheses

#### 2.3.1 Primary Safety Endpoint

The primary safety endpoint is whether or not any of the following adjudicated (see [Section 12](#)) events occur during the one month post intracoronary infusion:

1. Acute myocarditis possibly attributable to the investigational product (IP), diagnosed with consideration of clinical context, with or without a clinically indicated endomyocardial biopsy. In order to be considered related to the IP, humoral or cellular immune reaction specific to CAP-1002 must also be documented for subjects treated with CAP-1002, or a temporal relationship with IP administration must exist for subjects administered placebo. See [Section 12](#) for further information related to blinded adjudication by the Clinical Events Committee (CEC).
2. Death due to ventricular tachycardia or ventricular fibrillation defined as occurring with electrocardiogram (ECG) documentation of these arrhythmias during ambulatory ECG monitoring in an outpatient setting or during routine ECG monitoring while hospitalized.
3. Sudden unexpected death defined as occurring within one hour of symptom onset, or unwitnessed death in a person previously observed to be well within the preceding 24 hours without an identified cause.
4. Major adverse cardiac event (MACE), defined as the composite incidence of death, nonfatal recurrent MI, hospitalization with primary discharge diagnosis of heart failure, emergency room treatment for heart failure [ N-terminal pro-hormone brain natriuretic peptide (NT-proBNP)  $> 450$  pg/mL or brain natriuretic peptide (BNP)  $> 100$  pg/ml, with treatment including intravenous diuretic administration], LV assist device (LVAD) placement or heart transplant. Peri-infusion MI will be defined as presence of troponin or creatine phosphokinase MB isoenzyme (CK-MB) levels  $> 5$  times the upper reference limit during the 24 hours following infusion. These elevations must be accompanied by symptoms of ischemia  $> 20$  minutes in duration and ECG changes indicative of new ischemia (new ST-T changes or new left bundle branch block), development of pathological Q waves on the ECG, imaging evidence of new loss of viable myocardium, or new regional wall motion abnormality.

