### **2.3.3 Secondary Safety Endpoints**

The following adjudicated (see [Section 12](#)) events will be evaluated as secondary safety endpoints over the twelve-month follow-up period:

1. Acute myocarditis possibly attributable to the IP, diagnosed with consideration of clinical

context, with or without a clinically indicated endomyocardial biopsy. In order to be considered related to the IP, humoral or cellular immune reaction specific to CAP-1002 must also be documented for subjects treated with CAP-1002, or a temporal relationship with IP administration must exist for subjects administered placebo. See [Section 12](#) for further information related to blinded adjudication by the CEC.

2. Death due to ventricular tachycardia or ventricular fibrillation defined as occurring with prior ECG documentation of these arrhythmias during ambulatory ECG monitoring in an outpatient setting or during routine ECG monitoring while hospitalized.
3. Sudden unexpected death defined as occurring within one hour of symptom onset, or un-witnessed death in a person previously observed to be well within the preceding 24 hours without an identified cause.
4. MACE, as defined above.
5. New cardiac tumor formation on magnetic resonance imaging (MRI).
6. Any hospitalization due to a cardiovascular (CV) cause or related to IP infusion.
7. Any inter-current CV illness, or one related to IP infusion, which prolongs hospitalization. Evidence of myocardial injury will be assessed by a rule out MI cardiac enzyme protocol performed following IP administration. Troponin and CK-MB will be obtained approximately every 8 hours for the first 24 hours after infusion.
8. New TIMI flow  $\leq 1$  following IP infusion.
9. Development of, or an increase in the frequency of, ventricular tachycardia with a duration of 30 beats or longer ascertained by periodic, protocol-mandated 24 hour ambulatory ECG monitoring.

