## 10.5 Laboratory Evaluations

Listings of laboratory evaluations will include study visit, date and time of collection, normal ranges, and observed values with out-of-range values flagged. Separate series of listings will show out-of-range observations.

Observed values and changes from baseline will be summarized by study visit. Separate series of summaries will show incidence of out-of-range observations by study visit. Shift tables will summarize shifts from one out-of-range category at baseline to another out-of-range category at each subsequent study visit and will include p-values for treatment group differences.

Because local laboratories will be used for this study, units for some parameters may not be consistent across all laboratories; therefore, laboratory observations will be converted to standard units, if necessary, for summaries. [Appendix B](#) lists all clinical laboratory evaluations that will be done for this study and the corresponding standard units (evaluations listed without units are unitless).

Listings and summaries will be done separately for each of the following laboratory evaluations or groups of evaluations:

- Serum chemistry
- Hematology
- Urinalysis
- Coagulation (infusion visit only)
- Cardiac biomarkers (troponin I or troponin T, NT-proBNP)
- DSA monitoring
- ELISpot in a subset of subjects

For ELISpot, Cellular Technology Limited (CTL) will provide assay results for cells from test antigen cardiac cell lines in fetal bovine serum (FBS) containing medium, cells in serum-free medium, each in triplicate, and the positive control [phytohemagglutinin (PHA)] in a single well. Let  $X$  = average spot number to the given antigen (cells and antigen),  $SD(X)$  = SD of the three values for the antigen,  $Y$  = average spot number in the FBS-medium control (cells and no antigen), and  $SD(Y)$  = SD of the three values for the FBS-medium control. Then, the antigen specific value is:

$$X - SD(X) - [Y + 2SD(Y)]$$

A positive antigen specific response is defined as an antigen specific value  $> 3$ . All negative antigen specific values will be reported as 0 spot values since negative values are biologically irrelevant. The values of  $X$ ,  $SD(X)$ ,  $Y$ ,  $SD(Y)$ , antigen specific value, and antigen specific response will also be provided by CTL.

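### On CAP-1002, myocarditis needs a documented immune reaction, but the cellular assay is planned for at most 36 of 69 Primary Cohort subjects and stops at Month 1, so an antibody-negative, untested, non-MACE case cannot count.

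*Protocol*

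**What the plan says.** **Definition.** Acute myocarditis is item 1 of the primary safety endpoint. To be attributed to treatment on CAP-1002, SAP 2.3.1 requires that "humoral or cellular immune reaction specific to CAP-1002 must also be documented for subjects treated with CAP-1002". For the control arm, Protocol 9.5.1 asks only that "a temporal relationship with IP administration must exist for subjects administered placebo". The same item, with the same two rules, recurs at 12 months: Protocol 9.6.1 lists adjudicated events that "will be evaluated as secondary safety endpoints during the twelve-month follow-up period", and SAP 2.3.3 says that the adjudicated "events will be evaluated as secondary safety endpoints over the twelve-month follow-up period".

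**Cellular evidence.** ELISpot is the only cellular assay named. Protocol 6.5.2: "The ELISpot assay will be performed at screening and at the one month study visit in a total of 50 patients treated with CAP-1002", with the tested subjects split as "14 open-label CDC subjects, 36 randomized CDC subjects, 18 randomized placebo subjects". If the DSMB sees value in a larger sample, "ELISpot testing will be performed for additional subjects, followed by additional, subsequent DSMB review". SAP 10.5 lists "ELISpot in a subset of subjects". Protocol 7.1, 7.3.2 and Appendix 1 (and SAP Appendix A) show ELISpot at screening and Month 1 with no subset limit. Protocol 7.3.4 to 7.3.6 (Months 3, 6 and 12) contain no ELISpot.

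**Humoral evidence.** DSA monitoring is listed at screening, Week 2 and Months 1, 3, 6 and 12, with no subset limit.

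**Adjudication and missing data.** Under SAP 12, the events committee refers potential myocarditis to the DSMB, which sees the immunology data and rules on whether the event fits the protocol's definition. SAP 10.1 declares missing-data handling not applicable to the primary safety endpoint.

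**The concern.** The CAP-1002 rule makes documentation a condition of counting, but the plan does not collect one of the two kinds of documentation for about half the arm, or for anyone after Month 1. No rule covers a suspected case with no cellular result, and no unscheduled ELISpot for such a case is described. Under a rule that a reaction must be documented, not tested and tested negative lead to the same score.

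This is the event most specific to an allogeneic cell product. The definition accepts a humoral or a cellular reaction, so the plan itself regards a cellular-only case as qualifying. The loss falls on one arm only, because a placebo case needs no assay. Any error therefore lowers the CAP-1002 count and shifts the between-arm difference in its favour.

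**Working it through.** **1. Reproduce the plan's own figure.** Protocol 6.5.2: 14 open-label + 36 randomised = 50 CAP-1002 subjects with ELISpot. This matches. The randomised split 36:18 is 2:1, the allocation ratio.

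**2. Denominator.** 103 × 2/3 = 68.7; the Protocol synopsis gives 69 on CAP-1002 in the Primary Randomized Cohort.

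**3. Planned coverage at one month.**
- Tested: 36/69 = 52%. Untested: 69 − 36 = 33, and 33/69 = 48%.
- This is the best case for the Primary Cohort, because 6.5.2 does not confine the 36 to it. The Exploratory Cohort could add 17 × 2/3 ≈ 11 CAP-1002 subjects; over 69 + 11 = 80, coverage is 36/80 = 45%.

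**4. Planned coverage after Month 1.** None. The last scheduled sample is at Day 30 ± 3, while the secondary endpoint runs to 12 months.

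**5. Share of cases that could not qualify.** Let h be the share of CAP-1002 myocarditis cases that also show DSA. The documents give no value, so it is varied. Cases meeting a MACE component are set aside. Assume that testing is unrelated to risk. At one month the share is (1 − h) × 33/69. After Month 1 it is (1 − h), if a Month 1 ELISpot is not accepted for a later event.

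| h | One month | After Month 1 |
|---|---|---|
| 0 | 48% | 100% |
| 0.25 | 36% | 75% |
| 0.50 | 24% | 50% |
| 0.75 | 12% | 25% |

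**6. Effect on the rate.** One uncounted case is 1/69 = 1.4 percentage points. The documents give no incidence, so let q be an assumed one-month rate of DSA-negative, non-MACE myocarditis on CAP-1002, with every tested case detected. Expected uncounted cases are 33q, the apparent rate is 36q/69, and the chance of at least one uncounted case is 1 − (1 − q)^33.

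| Assumed q | Expected uncounted | Apparent rate | Chance of at least one |
|---|---|---|---|
| 2% | 0.7 | 1.0% | 49% |
| 5% | 1.7 | 2.6% | 82% |
| 10% | 3.3 | 5.2% | 97% |

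Even at 10% the understatement is 10 − 5.2 = 4.8 points. An understatement as large as the 0.20 margin in SAP 2.3.2 would need 0.20 × 69 = 13.8 uncounted cases.

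**7. What a zero count would mean.** If no cellular-only case is recorded, the one-sided 95% upper bound is 1 − 0.05^(1/36) = 8.0% on the 36 tested, not the 1 − 0.05^(1/69) = 4.2% that a denominator of 69 would suggest.

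**The case against.** The case against is substantial, and most of it limits the point.

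- **The humoral route is open to everyone throughout.** A reader might infer that every cell-mediated case outside the 36 is lost. The documents do not support that: a case with DSA still counts.
- **MACE is a separate component.** A case that leads to death, heart-failure hospitalisation or another MACE event enters the composite through item 4. It would still be absent from the myocarditis line, which SAP 10.1 reports separately.
- **The DSMB makes the final ruling.** A reader might infer that the plan instructs that untested be scored as negative. It does not; it is silent. But the DSMB rules against the protocol definition and has no cellular data for an untested subject, so its access does not close the gap.
- **The limit of 36 is not firm.** The DSMB may extend testing, and other protocol sections list ELISpot without a limit. But extension is discretionary and is not tied to a suspected case, the SAP says subset, and neither reading adds an assay after Month 1.
- **Biopsy might supply cellular evidence.** Protocol 7.3.2 allows it at any time if clinically indicated. The documents do not say that it can show a reaction specific to CAP-1002, and they do not exclude it.
- **Uncounted cases do not vanish.** They remain adverse events; serious or treatment-related ones are adjudicated, and cardiovascular hospitalisation is its own secondary endpoint. This protects visibility, not the endpoint count.

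**Conclusion.** The point holds for a defined group: clinically diagnosed myocarditis on CAP-1002 with no DSA, no ELISpot result and no MACE component. Under the rule as written such a case cannot qualify. On the 6.5.2 plan, 48% of Primary Cohort CAP-1002 subjects have no scheduled ELISpot at one month, and nobody has one afterwards. The direction is certain, because the gap can only reduce the CAP-1002 count.

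The size is modest. A reader might take 48% as the share of all myocarditis that is missed; it applies only to cases with no DSA and no MACE component, and falls to 36–12% if 25–75% of cases also show DSA. A reader might also infer that the trial's safety conclusion is compromised. That is not shown: no incidence is given, each case is worth about 1.4 points against a margin of 20, and the 12-month endpoint is a comparison of rates with no margin. The figures assume the base plan in 6.5.2 without DSMB extension, and testing unrelated to risk. The inconsistency over who is tested is a separate, plain contradiction between protocol sections.

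**What to change.** 1. **Definition.** In Protocol 2.4, 9.5.1 and 9.6.1 (and the matching synopsis text) and in SAP 2.3.1, 2.3.3 and 12, state that an absent ELISpot result is not read as a failed immune criterion. A case with no DSA and no ELISpot result counts on adjudicated clinical diagnosis plus temporal relationship with the investigational product, the criterion already used for placebo. Flag it 'cellular immunity not assessed' and report the number. State also what counts as absent for a late event (whether a Month 1 result applies) and what temporal relationship means over 12 months, which the documents leave undefined.
2. **Sensitivity analysis.** For the 1-month and 12-month endpoints, report all adjudicated clinical myocarditis in both arms regardless of immune documentation. This matters because step 1 alone would leave two rules within the CAP-1002 arm, one for untested and one for tested-negative subjects.
3. **Coverage.** Reconcile Protocol 6.5.2 with 7.1, 7.3.2 and Appendix 1 on who has ELISpot.

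**Cost.** No new assay or visit. It does change an endpoint definition, so it needs a protocol amendment or an entry in SAP 14, which now declares no deviations; SAP wording alone would contradict the protocol. It also needs one flag and a few table rows, settled before unblinding. The CAP-1002 count may be slightly less favourable, and untested cases would be attributed less specifically.
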